The Phase 2a study D5495C00007 was performed using 9 mg verinurad given as the ER8 capsule and 80 mg febuxostat administered once daily in combination for 24 weeks. The primary endpoint was UACR at 12 weeks.

Sixty patients were randomised. At enrolment, the treatment arms in study D5495C00007 were generally balanced with regards to common clinical parameters.

The study met the primary endpoint at 12 weeks. UACR was significantly reduced by 39.4% for patients randomised to be treated with verinural and febuxostat compared to placebo (p=0.0747). The comparison between the active arm and the control arm indicated statistical significance was achieved, considering the predetermined alpha (0.1). The effect on UACR was rapid, with full effect achieved at the first on-treatment assessment time point at 1 week, and did not appear to be driven by outliers. The therapeutic effect persisted with an LS mean of percent change from baseline in UACR compared to placebo (90% CI) -49.26 (-68.206, -19.009) at Week 24.

Mean baseline eGFR in the trial was 59 and 68 mL/min/ 1.73 m^2 in the active and control arms, respectively. There were no changes in eGFR in either arm, either at the early or late assessment time points. However, considering the limited sample size, eGFR variability, and short duration of treatment, this is not unexpected. Overall the treatment was well tolerated and safety findings in the study were consistent with the known safety profile of the drug.

The overall clinical evidence suggests that the combination of verinurad and XOI has clinical benefit and an acceptable safety profile in CKD patients and that further development is warranted. Hence, a global, randomised, Phase 2b study is planned to evaluate the efficacy and safety of verinurad and allopurinol in patients with CKD and hyperuricaemia.

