9 STATISTICAL CONSIDERATIONS

9.1 Statistical hypotheses

Three hypotheses will be included in confirmatory testing for the primary objective. See Section 9.4.4 for a description of multiplicity control. The following hypotheses will be tested sequentially at two-sided alpha = 0.1 (treatments refer to initial dosing regimen prior to Protocol Version 5.0):

- Null hypothesis: No difference between high dose verinurad plus allopurinol compared to placebo on UACR at 6 months
- Alternative hypothesis: There is a difference between high dose verinurad plus allopurinol compared to placebo on UACR at 6 months
- Null hypothesis: No difference between high and intermediate dose verinurad combined plus allopurinol compared to allopurinol alone on UACR at 6 months
- Alternative hypothesis: There is a difference between high and intermediate dose verinurad combined plus allopurinol compared to allopurinol alone on UACR at 6 months

- Null hypothesis: No difference between allopurinol alone compared to placebo on UACR at 6 months
- Alternative hypothesis: There is a difference between allopurinol alone compared to placebo on UACR at 6 months

No other comparisons between treatment groups for the primary and secondary objectives will be adjusted for multiplicity.

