9.4.2.1 Primary efficacy analysis

The primary efficacy variable is the change from baseline in UACR at 6 months (Week 34, ie, 26 weeks of treatment following an 8-week titration phase). Primary analyses will be performed on the FAS population, which consists of all randomised patients regardless of

treatment discontinuation. In other words, post-discontinuation data will be collected and included in the primary analysis. Details on how to handle missing data will be provided in the SAP.

In addition to analysis of the hypotheses in Section 9.1, the primary efficacy variable will be analysed comparing (initial dosing regimen):

- Intermediate dose verinurad plus allopurinol with placebo
- Low dose verinurad plus allopurinol with placebo
- High dose verinurad plus allopurinol with allopurinol alone
- Intermediate dose verinurad plus allopurinol with allopurinol alone
- Low dose verinurad plus allopurinol with allopurinol alone

The analysis of change in UACR from baseline to Week 34 will be conducted on the natural log-transformed UACR values using a repeated measures mixed model.

The analysis model will include the fixed categorical effects of treatment, week, DM status yes or no, microalbuminuria or macroalbuminuria, NT-proBNP < or \geq 360 pg/mL, use of SGLT2 yes or no, and treatment-by-week interaction as well as the continuous fixed covariates of baseline log(UACR) and baseline log(UACR) by-week interaction. An unstructured matrix for the within patient error variance-covariance will be used. The denominator degrees of freedom will be calculated according to the Kenward-Roger method. A number of back-up models will be defined in the SAP in case of non-convergence of the preferred model or other issues.

The least squared mean change from baseline to 6 months in the log-transformed UACR will be calculated by treatment with its 95% confidence intervals. The least squared mean difference between the treatments will be calculated with its 95% confidence interval. P-values of the treatment differences between active treatment group and placebo/comparator will also be calculated.

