The above least squared mean change from baseline (and the 95% confidence interval) for each treatment will be exponentiated to yield the geometric mean ratio from baseline for each treatment with its 95% confidence interval at the original scale of UACR. The least squared mean difference between the active treatments and placebo/comparator (and its 95% confidence interval) will also be exponentiated to yield the geometric mean ratio between the 2 treatments at each visit and its 95% confidence interval at the original scale of UACR. Percent change from baseline will be derived from the geometric estimated mean ratio by ([geometric mean ratio] - 1) \times 100%.

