9.4.4 Methods for multiplicity control

The experiment-wise Type I error will be controlled at 10% by hierarchical testing of the hypotheses in Section 9.1. No other comparisons will be adjusted for multiplicity.

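### The three hierarchical primary contrasts are tested at two-sided alpha 0.10 but planned with 95% intervals only, so a rejected null hypothesis can be reported with an interval that includes no effect

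*Supplement*

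**What the plan says.** Section 9.1 lists three confirmatory contrasts on UACR at 6 months: high dose plus allopurinol versus placebo, high and intermediate doses combined versus allopurinol alone, and allopurinol alone versus placebo. On the level it says: "The following hypotheses will be tested sequentially at two-sided alpha = 0.1". Section 9.4.4 confirms the overall rate: "The experiment-wise Type I error will be controlled at 10% by hierarchical testing of the hypotheses in Section 9.1". Section 9.2 sizes the trial at the same alpha.

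Section 9.4.2.1, which analyses these contrasts, sets a different confidence level. On the log scale: "The least squared mean difference between the treatments will be calculated with its 95% confidence interval". After back-transformation: "The least squared mean difference between the active treatments and placebo/comparator (and its 95% confidence interval) will also be exponentiated". It also plans p-values: "P-values of the treatment differences between active treatment group and placebo/comparator will also be calculated".

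The protocol plans no 90% interval anywhere. Nothing in it says that the 95% intervals are descriptive or that conclusions do not rest on them. The only 90% interval in the document, in Section 2.1, belongs to the earlier Phase 2a study, which was also judged at alpha 0.1.

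**The concern.** A two-sided test at 0.10 and a two-sided 90% interval from the same model give the same answer: the interval excludes a ratio of 1 exactly when p is below 0.10. A 95% interval excludes 1 only when p is below 0.05. Between those two values the protocol's rule rejects the null and opens the next hypothesis, while the only interval planned for that contrast spans no effect.

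What is at stake is how the primary result reads. With p between 0.05 and 0.10, one reader would follow the test and call the contrast positive, and another would follow the interval and call it inconclusive. The protocol does not say which display carries the conclusion. If the interval level were chosen only after such a p-value had been seen, the choice would look data-driven.

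**Working it through.** **Inputs.** From Section 9.2: 145 per arm, SD 1.0 on the natural log scale, a 25% reduction (given as about -0.29; exactly ln 0.75 = -0.2877), two-sided alpha 0.10, 80% power. From Section 9.4.2.1: 95% intervals.

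**Reproducing the sample size.** With the normal approximation, n per arm = 2(z_alpha + z_beta)² / delta².
- Alpha 0.10, delta 0.29: 2(1.645 + 0.842)² / 0.29² gives 148. Power at 145 is 79.5%.
- Alpha 0.10, delta 0.2877: n is 150. Power at 145 is 78.9%.
- Alpha 0.05: n would be 187 (delta 0.29) or 190 (delta 0.2877).

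So 145 is close to the figure for alpha 0.10 and far from the figure for alpha 0.05. The trial was sized at the level at which it tests.

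**The band for high dose versus placebo.** SE = sqrt(2/145) = 0.1174.
- Smallest observed reduction with p < 0.10: 1 - exp(-1.645 × 0.1174) = 17.6%.
- Smallest observed reduction whose 95% interval excludes 1: 1 - exp(-1.960 × 0.1174) = 20.6%.

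An observed reduction between 17.6% and 20.6% rejects the null with a 95% interval that includes 1. Allopurinol versus placebo also compares 145 with 145, so it has the same band.

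**Example.** For an observed reduction of 19%, ln 0.81 = -0.2107 and z = 0.2107 / 0.1174 = 1.79, so p = 0.073. The 90% interval for the ratio is 0.668 to 0.983. The 95% interval is 0.643 to 1.020.

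**The band for the pooled doses versus allopurinol alone.** SE = sqrt(1/290 + 1/145) = 0.1017. The limits are 1 - exp(-1.645 × 0.1017) = 15.4% and 1 - exp(-1.960 × 0.1017) = 18.1%.

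**How often, for high dose versus placebo, if the planning alternative is true.** The probability of landing in the band is the power at alpha 0.10 minus the power at alpha 0.05.
- Delta 0.2877: 0.789 - 0.688 = 0.102 (from unrounded values).
- Delta 0.29: 0.795 - 0.695 = 0.100.
- A noncentral t calculation gives 0.103 and 0.102 respectively.

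That is about 10% of trials. As a share of rejections it is 0.102 / 0.789 = 0.13, or about one in eight.

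**The Phase 2a result as an illustration.** Section 2.1 reports a 39.4% reduction with p = 0.0747, called significant at 0.1. By normal approximation, z = 1.782 and SE = |ln 0.606| / 1.782 = 0.501 / 1.782 = 0.281. The implied 90% interval is about -61.8% to -3.8%, and the implied 95% interval about -65.1% to +5.1%. These are back-calculated. The protocol gives no interval for that 12-week result; the 90% interval it does quote is for Week 24.

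**The case against.** The strongest reply is that no decision depends on the interval. Rejection and movement down the hierarchy rest on the test at 0.10, and p-values are planned beside the intervals. This stands in full. A reader might infer from the mismatch that the error rate or the power is wrong, or that the estimate contradicts the conclusion. The documents support neither. The point estimate is the same at any confidence level, and a 95% interval that includes 1 is a stricter statement, not a contradiction of rejection at 0.10. A careful reader could also recover an approximate 90% interval by shrinking the log-scale half-width by 1.645/1.960.

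A second reply is that 95% is conventional and that most comparisons in the protocol are not confirmatory. This also stands, and it limits the point. A reader might infer that every treatment difference is affected. Only the three contrasts in Section 9.1 carry alpha 0.10. The five further primary comparisons in Section 9.4.2.1 and the secondary comparisons in Section 9.4.2.2 are unadjusted and have no stated test level, so 95% intervals there conflict with nothing.

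A third reply is that Section 9.4 describes itself as a summary and leaves detail to the SAP, which is not among the documents reviewed. The SAP could add 90% intervals. The protocol, however, did not leave the level open; it fixed it at 95%, and that text would still need to be aligned.

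Finally, the Phase 2a study shows that such a result is plausible, but its interval level does not bind this trial.

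**Conclusion.** The mismatch holds for the three hierarchical contrasts. For any p between 0.05 and 0.10, the null is rejected while the planned interval includes a ratio of 1. This follows from the two stated levels and needs no assumption about the data.

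The size is illustrative. The 17.6% to 20.6% band and the probability of about 10% assume that all 145 per arm are observed at Week 34, a residual SD of exactly 1.0, and a simple two-sample comparison. The planned model is a covariate-adjusted repeated measures model, and some data will probably be missing, so the real band will sit elsewhere; it cannot vanish. The 10% counts trials whose test and planned interval would point different ways, not trials with a wrong conclusion.

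Severity is minor to moderate. This is a flaw in how the primary result would be reported, not in inference or design.

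**What to change.** In Section 9.4.2.1, state that for the three contrasts in Section 9.1 the least squares mean difference on the log scale and the geometric mean ratio will be reported with two-sided 90% confidence intervals, matching the test level. If 95% intervals are also wanted for these contrasts, keep them as additional output labelled descriptive. The 95% intervals for the non-confirmatory comparisons can stay. Carry the same wording into the SAP if it repeats the 95% level.

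A sentence saying that conclusions rest on p < 0.10 and that the 95% intervals are descriptive would remove the ambiguity, but it would still leave the matching interval unreported.

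The cost is one sentence and a table-shell change. Sample size, alpha, power and trial conduct do not change. The change should be made before unblinding.

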9.4.2.2 Secondary efficacy analyses

For the secondary variables at 6 months, the following comparisons will be made (initial dosing regimen):

- High dose verinurad plus allopurinol with placebo
- Intermediate dose verinurad plus allopurinol with placebo
- Low dose verinurad plus allopurinol with placebo
- High dose verinurad plus allopurinol with allopurinol alone
- Intermediate dose verinurad plus allopurinol with allopurinol alone
- Low dose verinurad plus allopurinol with allopurinol alone
- Allopurinol with placebo

For the secondary variables at 12 months, the comparison "24 mg (double dose)" versus "Placebo (double dose)" will be made. If the model will not provide reliable results (eg, due to no convergence), descriptive statistics only will be considered sufficient.

All secondary variables will be log-transformed before analysis.

Analysis of secondary variables at 6 and 12 months will be performed using a model similar to that used for the primary efficacy variable. Change from baseline and treatment comparisons will also be estimated similarly.

The dose response of verinural plus allopurinol on UACR and sUA will be evaluated using modelling, and the details will be provided in the SAP.

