9.2 Sample size determination

The estimated sample size of 145 patients per arm (initial dosing regimen) will yield 80% power to detect a 25% reduction in UACR for the high dose of verinurad + allopurinol compared to placebo (treatment difference of approximately -0.29 on the natural log scale) at the two-sided alpha level of 0.1, assuming a standard deviation of 1.0 on the natural log-scale. A total of 725 patients (145 patients per arm [initial dosing regimen]) must be randomised. The standard deviation estimate is based on the results of Study D5495C00007.

For the MRI substudy, a sample size of 30 in each arm (initial dosing regimen) will have at least 80% power to detect a difference (high dose verinurad + allopurinol vs. placebo) in means of 0.05 in renal arterial resistive index assuming that the common standard deviation is 0.05 with a 0.05 two-sided significance level. The standard deviation of 0.05 is based on data published by Leoncini et al 2002.

9.3 **Populations for analyses**

For purposes of analysis, the following populations are defined in Table 16:

Population	Description
Enrolled	All patients who sign the main ICF
Randomised set	All patients who are randomised
Full Analysis Set	All randomised patients
PPS	The per-protocol analysis set is a subset of the Full Analysis Set consisting of all patients who do not violate the terms of the protocol in a way that may affect the primary efficacy endpoint significantly. All decisions to exclude patients from the per-protocol analysis set will be made prior to the un- blinding of the study.
Efficacy analysis set	Full analysis set
Safety analysis set	All patients who had at least 1 dose of IP.
PK set	All patients who received allopurinol and verinurad treatment and have at least one post-dose plasma concentration measurement of verinurad at a scheduled time point

Table 16Analysis populations

ICF Informed consent form; IP Investigational product; PK pharmacokinetic

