9.4 Statistical analyses

All personnel involved with the analysis of the study will remain blinded until database lock.

Analyses will be performed by a CRO designated by AstraZeneca. A comprehensive statistical analysis plan (SAP) will be developed and finalised before the first interim analysis and will describe the subject populations to be included in the analyse and procedures for accounting for missing data. This section is a summary of the planned statistical analyses. Any deviations from this plan will be reported in the CSR.

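### The 12-month comparison of 24 mg with placebo may fall back to descriptive statistics on an undefined reliability judgement, while the primary model gets back-up models

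*Supplement*

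**What the plan says.** Only the protocol (version 5.0) is among the documents; no SAP is shown.

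- **The comparison.** Section 9.4.2.2: "For the secondary variables at 12 months, the comparison '24 mg (double dose)' versus 'Placebo (double dose)' will be made".
- **The model.** Same section: "Analysis of secondary variables at 6 and 12 months will be performed using a model similar to that used for the primary efficacy variable". Section 9.4.2.1 specifies that primary model as a repeated-measures mixed model with unstructured covariance and Kenward-Roger degrees of freedom.
- **The fallback.** Immediately after naming the 12-month comparison, section 9.4.2.2 states: "If the model will not provide reliable results (eg, due to no convergence), descriptive statistics only will be considered sufficient".
- **The rule for the primary model.** Section 9.4.2.1: "A number of back-up models will be defined in the SAP in case of non-convergence of the preferred model or other issues".
- **Status.** The comparison is not one of the three hypotheses in section 9.1, and section 9.4.4 says: "No other comparisons will be adjusted for multiplicity".
- **Blinding.** Section 9.4: "All personnel involved with the analysis of the study will remain blinded until database lock".

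**The concern.** The protocol sets two different responses to the same fitting problem. If the primary model fails, other models are tried. If the 12-month model fails, descriptive output is enough, and no simpler model need be attempted.

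The trigger is also open. Non-convergence can be checked by anyone, but it is given only as an example of a wider, undefined category. No criterion, decision-maker or timing is stated. A model that compares treatments can be judged only once it has been fitted with treatment codes, and analysis staff have those only after database lock. The wording therefore allows the decision to follow sight of the estimate.

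At stake is the model-based, baseline-adjusted ratio of 24 mg to placebo with its interval. Assessing 24 mg was a main reason for version 5.0. The dose is first given at Week 47 (Visit 9), so no 6-month (Week 34) comparison can inform it. In the visible text this is the only planned efficacy comparison that includes it.

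**Working it through.** The point is textual, so the main check sets the two rules side by side.

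| | Primary model (9.4.2.1) | 12-month model (9.4.2.2) |
|---|---|---|
| Trigger | Non-convergence or other issues | Results not reliable; non-convergence as an example |
| Response | Back-up models, to be defined in the SAP | Descriptive statistics are enough |
| Adjusted estimate and interval kept? | Yes, if a back-up model fits | Not required |

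Both triggers are open-ended. The difference lies in the response.

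**The plan's own figure.** Section 9.2 says that 145 per arm "will yield 80% power to detect a 25% reduction in UACR for the high dose of verinurad + allopurinol" compared with placebo, "at the two-sided alpha level of 0.1, assuming a standard deviation of 1.0 on the natural log-scale". With n = 2(1.645 + 0.842)² × SD² / δ²:

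- δ = 0.29 (the rounded value in the protocol): n = 148 per arm; power at 145 is 79.5%.
- δ = −ln(0.75) = 0.2877: n = 150 per arm; power at 145 is 78.9%.

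The stated design is reproduced closely enough. It concerns the 6-month comparison of the high dose with placebo. The documents give no sample size or power for 24 mg.

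**Illustration of what an adjusted comparison would offer.** Inputs:

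- SD 1.0 on the natural log scale (section 9.2), assumed to hold at Week 60 as well.
- About 72 per arm, which is half of 145. Section 4.1.1 says only that roughly half of planned patients come under the new regimen, so this is an assumption. It is close to a ceiling, because patients who were down-titrated, did not consent, or had eGFR below 30 mL/min/1.73 m² at Visit 8 do not switch.
- 95% intervals, the level specified in section 9.4.2.1.

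SE = SD × √(2/n), and the interval around a ratio of 1 is exp(±1.96 × SE).

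| n per arm | SE | 1.96 × SE | 95% interval |
|---|---|---|---|
| 72 | 0.167 | 0.327 | 0.72 to 1.39 |
| 50 | 0.200 | 0.392 | 0.68 to 1.48 |
| 36 | 0.236 | 0.462 | 0.63 to 1.59 |

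If the design effect of a 25% reduction also applied at 12 months, power with 72 per arm would be about 53% at two-sided alpha 0.1 and 41% at 0.05. With 36 per arm it would be about 34% and 23%.

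These figures show the precision of the estimate that might be lost. They do not measure how likely the model is to fail, or how much bias the discretion could introduce.

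**The case against.** The best defence is that section 9.4 calls itself a summary and defers to a comprehensive SAP. That SAP could define reliability and extend the primary back-up models to a model described as similar. Calling descriptive statistics sufficient sets a minimum and does not forbid trying simpler models. Section 9.4.2.4 uses much the same wording for subgroups.

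This has some force, and an SAP that does these things would largely settle the matter. But the point does not rest on missing SAP detail. It concerns a rule that the protocol states itself, and that rule accepts descriptive output without any further attempt. The subgroup analyses supplement a primary result, whereas no other 24 mg contrast is visible here.

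Four stronger readings are tempting, and the documents do not support them:

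- **That the 24 mg question would go unanswered.** Descriptive results would still be reported. The contrast covers five separate variables (UACR, sUA, eGFR, creatinine, cystatin-C), and one failed fit does not lose the others.
- **That no other 24 mg efficacy analysis exists.** Exploratory text is redacted, so this can be said only of the visible text.
- **That the fallback makes any interval impossible.** Section 9.4.2 lists means and SDs among its descriptive statistics and leaves the list open. An unadjusted difference could be derived if log changes are summarised by arm. What is lost is the planned adjusted contrast.
- **That someone means to drop an unwelcome result.** The wording permits a decision after unblinding; nothing suggests intent.

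It is also right that non-convergence should not be the sole trigger. A fit can converge nominally yet have a degenerate covariance or Hessian, and it should not then be reported as sound.

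**Conclusion.** The concern holds in a limited form. Section 9.4.2.2 lets the adjusted 12-month comparison of 24 mg with placebo, and its confidence interval, give way to descriptive statistics on an undefined standard, while the primary model has back-up models for the same problem.

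It is a minor point, worth mending because the remedy is nearly free. The comparison is secondary and unadjusted for multiplicity, and the three confirmatory hypotheses are untouched. The estimate at risk would be imprecise in any case: about 0.72 to 1.39 around a ratio of 1, assuming at most about 72 per arm and SD 1.0, and wider with fewer patients switching. The conclusion rests on the protocol wording and does not depend on these figures.

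**What to change.** Replace the fallback sentence in section 9.4.2.2 with a rule fixed before unblinding:

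1. **Objective triggers.** Leave the preferred model only for non-convergence, or for a non-positive-definite covariance or Hessian. Remove the general appeal to reliability.
2. **Ordered back-ups.** Apply the primary analysis's back-up models to the 12-month model in a stated order. The intermediate covariance structures are the sponsor's choice. If a back-up uses a robust variance, state the degrees-of-freedom method, since Kenward-Roger as specified would not carry over directly.
3. **Last step.** Fit an ANCOVA of log change at Week 60 on treatment, baseline log value and the same categorical factors as the primary model, reported with its 95% interval. It needs no iterative covariance fit. It uses only patients with a Week 60 value, so report how many are excluded.

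Descriptive statistics can accompany whichever model is used. The cost is a sentence or two in the protocol or SAP and a few lines of program, with no effect on patients, visits or sample size.
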